4.14.5 The Stratified Wilcoxon-Mann-Whitney Test Statistic

Let $x_k = (x_{k,1}, \dots, x_{k,m_k})$ and $y_k = (y_{k,1}, \dots, y_{k,n_k})$, $k = 1, \dots, d$, be the d pairs (strata) of independent random samples from distribution F_k and G_k , respectively, where d is the number of blocks of baseline score. The x -values are from the active test group, and the y -values are from the placebo group.

The null hypotheses of superiority test can be expressed as

$$H_0: \pi = 0.5$$

where $\pi = \sum_{k=1}^d c_k \Pr(Y_k > X_k)$, X_k and Y_k are random variables with distribution F_k and G_k , respectively, and $c_k = m_k n_k (m_k + n_k + 1)^{-1}$.

The stratified WMW test statistic (van Elteren statistic) is computed as

$$T = \frac{\hat{\pi} - 0.5}{\sqrt{v_0}}$$

where

$$\begin{aligned}\hat{\pi} &= \sum_{k=1}^d c_k W_k \\ W_k &= (m_k n_k)^{-1} \sum_{i=1}^{m_k} \sum_{j=1}^{n_k} I(y_{k,j} > x_{k,i})\end{aligned}$$

and

$$v_0 = \sum_{k=1}^d c_k^2 (12m_k n_k)^{-1} (m_k + n_k + 1).$$

The detail can be seen in Qu et al. (2008).

The SAS syntax of stratified WMW test (Van Elteren test) is specified as follows:

```
PROC NPAR1WAY DATA = <input_dataset> ;  
CLASS trt01pn ;  
STRATA baseline_score;  
VAR Change_from_baseline;  
RUN;
```

where `input_data` = “Individual efficacy data of changing from baseline”

`trt01pn` = “treatment group, 1 stands for test group; 2 stands for control group”
`baseline_score` = “The following Baseline score will be implemented separately, including sputum viscosity score, expectoration difficulty score, sputum color score, cough severity score and sputum volume”

Change_from_baseline= “The response will consider : (1) Change from baseline to day 3 (2) Change from baseline to day7. For each condition, the following change from baseline score will be considered: sputum viscosity score, expectoration difficulty score, sputum color score, cough severity score, sputum volume.”

4.14.6 The Modified Wilcoxon-Mann-Whitney Test Statistic

Let $x = (x_1, \dots, x_{n_T})$ and $y = (y_1, \dots, y_{n_C})$ denote the independent random samples from distribution F_C and F_T , respectively. The x -values are from the active test group, and the y -values are from the active control group.

The null hypotheses of non-inferiority test are expressed as

$$H_0: p \leq 0.5 - \delta$$

where $p = Pr(X < Y) + 0.5 \times Pr(X = Y)$, and the value for δ is the non-inferiority margin.

The unbiased estimator of p is given by

$$\hat{p} = n_T^{-1}(\bar{R}_C - (n_C + 1)/2)$$

where \bar{R}_C is the arithmetic average of the rank of the observation in the active control group among all observations. That is $\bar{R}_C = \sum_{j=1}^{n_C} R(y_j)/n_C$, where $R(y_j)$ is the rank of y_j in ordering of the combined sample. Define also $\bar{R}_T = \sum_{j=1}^{n_T} R(x_j)/n_T$, where $R(x_j)$ is the rank of x_j in the ordering of the combined sample. When ties occur, $R(y_j)$ is the midrank, as well as $R(x_j)$. Let $R^{(C)}(y_j)$ denote the rank of y_j among y_1, \dots, y_{n_C} , and let $R^{(T)}(x_j)$ denote the rank of x_j among x_1, \dots, x_{n_T} . Define

$$J_T^2 = \sum_{j=1}^{n_T} (R(x_j) - R^{(T)}(x_j) - \bar{R}_T + (n_T + 1)/2)^2 / (n_T - 1),$$

and

$$J_C^2 = \sum_{j=1}^{n_C} (R(y_j) - R^{(C)}(y_j) - \bar{R}_C + (n_C + 1)/2)^2 / (n_C - 1).$$

Furthermore, for $i = T, C$, define $\hat{u}_i^2 = J_i^2 / (N - n_i)^2$, where $N = n_T + n_C$. The test statistics is given by

$$Q = \frac{\hat{p} - (0.5 - \delta)}{\sqrt{\frac{\hat{u}_c^2}{n_c} + \frac{\hat{u}_T^2}{n_T}}}.$$

The detail can be seen in (Munzel and Hauschke, 2003) as well.

Since for using Munzel and Hauschke approach, a non-inferiority margin expressed on a probability scale is needed, the non-inferiority margin (as used in the sample size estimation) needs to be converted from a point scale (since it is expressed in the same scale of data) to a probability scale.

The converted non-inferiority margin can be derived as below.

To derive δ'' (probability scale margin) from δ' (point scale margin) we apply the following formula of Cohen D effect size by assuming normality between two effect size:

$$\delta'' = \delta' \times \frac{SD(\delta'')}{SD(\delta')}$$

Where $\delta' = 0.30$; $SD(\delta') = \sqrt{\sigma_c^2 + \sigma_T^2}$; $SD(\delta'') = \sqrt{\mu_c^2 + \mu_T^2}$

- SD is the term used here to indicate the standard deviation associated to statistic based on δ' and δ''
- σ_c and σ_T are the standard deviation of the changes from baseline of the original scores for control group and test group respectively
- μ_c and μ_T are estimated according to the formula as shown above.

The SAS syntax of obtaining the probability margin converting from point scales and modified Wilcoxon-Mann Whitney test are specified as follows.

```
/*R(x j ) and R(y j )*/
proc rank data=input_data out=out1 ties=mean;
  var chg;
  ranks r_chg;
run;

data out1t;
  set out1;
  where trt01pn=1;
run;

data out1c;
  set out1;
  where trt01pn=2;
run;

/*R^((T) ) (x_j )*/
proc rank data=input_data (where=(trt01pn=1)) out=out_rt ties=mean;
  var chg;
  ranks r_chg_rt;
```

```
run;

/*R^((C) ) (y j )*/
proc rank data=input_data (where=(trt01pn=2)) out=out_rc ties=mean;
  var chg;
  ranks r_chg_rc;
run;

/*R mean T and  n_T*/
proc sql;
  select mean(r_chg), count(r_chg) into: avg_rt, :n_t
  from out1(where=(trt01pn=1));
quit;

%put &avg_rt &n_t;

/* R_mean C and  n_C*/
proc sql;
  select mean(r_chg), count(r_chg) into: avg_rc, :n_c
  from out1(where=(trt01pn=2));
quit;

%put &avg_rc &n_c;

/*JT2*/
proc sql noprint;
  select sum(((r_chg - r_chg_rt - &avg_RT + (&n_T+1)/2)**2)/(&n_T-1))
  into :JT2
  from out1 as a
  left join out_rt as b
  on a.usubjid = b.usubjid;
quit;
%put &JT2;

/*JC2*/
proc sql noprint;
  select sum(((r_chg - r_chg_rc - &avg_RC + (&n_C+1)/2)**2)/(&n_C-1))
  into :JC2
  from out1c as a
  left join out_rc as b
  on a.usubjid = b.usubjid;
quit;
%put &JC2;

/*UT2 and UC2*/
%let UT2=%sysevalf(&JT2/(&n_C**2));
%let UC2=%sysevalf(&JC2/(&n_T**2));

%put &UT2; %put &UC2;

/*Std_RC and Std_RT*/
proc sql;
  select std(chg) into : std_rc
  from out_rc;
quit;
```

```
%put &std_rc;  
  
proc sql;  
    select std(chg)  into : std_rt  
    from out_rt;  
quit;  
  
%put &std_rt;
```

All above calculated variables will be used to calculate the δ to implement the following modified Wilcoxon-Mann-Whitney tests.

The SAS syntax of modified Wilcoxon-Mann-Whitney test to compute test statistics and one side confidence intervals are specified as follows:

```
proc freq data= input_data; /*somers d statistics*/  
    table trt01pn*chg /measures;  
    test smdcr;  
    output smdcr out=smd_out;  
run;  
  
data outf;  
    set smd_out;  
    p_1=(1+ smdcr )/2; /* unbiased estimator of p */  
    e_p1=e_smdcr/2;  
    keep _smdcr_ e_smdcr p_1 e_p1;  
run;  
  
data test;  
    set outf;  
    delta1=0.3;  
    delta2= delta1*sqrt(&UT2+&UC2)/sqrt(&Std_RT**2+&Std_RC**2) ;  
    p_10=0.5- delta2 ; /* defined margin*/  
    Z_p1=(p_1-p_10)/e_p1; /* modified Wilcoxon-Mann-Whitney test  
    statistics*/  
  
    p_p1=1-probnorm(Z_p1); /*p value for P_1*/  
  
    lower limit_1=p_1-1.96* e_p1; /* Depends on results of primary  
    endpoint, here is the sample code of one side 97.5% lower CI of  
    modified Wilcoxon-Mann-Whitney test statistics */  
    upper limit_1=1; /* Upper CI of modified Wilcoxon-Mann-Whitney  
    test statistics*/  
  
    lower limit_2=p_1-2.24* e_p1; /* Depends on results of primary  
    endpoint, here is the sample code of one side 98.75% lower CI of  
    modified Wilcoxon-Mann-Whitney test statistics */  
    upper limit_2=1; /* Upper CI of modified Wilcoxon-Mann-Whitney  
    test statistics*/  
  
run;
```

where `input_data` = “individual efficacy data of changing from baseline”

trt01pn = “treatment group, 1 stands for test group; 2 stands for control group”
chg = “change from baseline score of ordinal categorical 4-point scales starting from 0(normal) to 3(worst) of sputum viscosity score, expectoration difficulty score, sputum color score, and cough severity score”

4.14.7 Partial Date Conventions

Imputed dates will not be presented in the listings.

However, in general, when calculating relative days, partial dates with missing day only will be assumed to be 15th of the month, and partial dates with both missing day and month will be assumed to be June 30.

Otherwise, the following rules in the given table will be applied for each case.

4.14.7.1 Algorithm for Prior/Concomitant Medications

Start Date	Stop Date	Action
Known	Known	If start and stop dates are prior to the date of first dose of study medication, considered as prior; If stop date is on or after the date of first dose of study medication, considered as concomitant.
	Partial	The last day of the month will be used if only the day of stop date is missing; Date of last dose of study medication will be used if day and month of stop date is missing; December 31st will be used if day and month of stop date is missing and the year of the year of last dose of study medication is greater than the year of stop date. If start date and the imputed stop date is prior to the date of first dose of study medication, considered as prior; if the imputed stop date is on or after the date of first dose of study medication, considered as concomitant.
	Missing	Stop date will not be imputed. Considered as concomitant.

Start Date	Stop Date	Action
Partial	Known	
January 1st will be used if the start day and month is missing and the year of first dose of study medication is not the same as the year of the start date;
 
the date of first dose of study mediation will be used if the start day and month is missing and the year of first dose of study medication is the same as the year of the start date;
 
the date of first dose of study mediation will be used if only the day of start date is missing, and the month and year of start date is the same as the first dose of study medication;
 
The first day of the month will be used if only the date of start date is missing, and the month and year of start date is not the same as the first dose of study medication.
 
If the imputed start date and stop date is prior to the date of first dose of study medication, considered as prior;
 
if the stop date is on or after the date of first dose of study medication, considered as concomitant.

	Partial	
The same imputation rule of partial start date when start date is partial, stop date is known will be applied;
 
the same imputation rule of partial stop date when start date is known, stop date is partial will be applied.
 
If the imputed start date and stop date is prior to the date of first dose of study medication, considered as prior;
 
if the imputed stop date is on or after the date of first dose of study medication and is up to the last dose of study medication, considered as concomitant.

	Missing	
The same imputation rule of partial start date when start date is partial, stop date is known will be applied;
 
The stop date will not be imputed.
 
Considered as concomitant.

Start Date	Stop Date	Action
Missing	Known	
The date of first dose will be used if stop date is not prior to the date of first dose of study medication.
 
Start date will not be imputed if stop date is prior to the date of first dose of study medication.
 
If stop date is prior to the date of first dose of study medication, considered as prior;
 
if stop date is on or after the date of first dose of study medication, considered as concomitant.

	Partial	
Start date will not be imputed;
 
the same imputation rule of partial stop date when start date is known, stop date is partial will be applied.
 
If the imputed stop date is prior to the date of first dose of study medication, considered as prior;
 
if the imputed stop date is on or after the date of first dose of study medication, considered as concomitant.

	Missing	
The date of first dose will be used to impute start date;
 
the stop date will not be imputed.
 
Considered as concomitant.

Note: If the recorded start date or imputed start date of the medication is after the date of last dose of study drug, it will not be classified to prior or concomitant medications, just set the category to missing.

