4.7 Prior and Concomitant Medication

Medication start and stop dates will be compared to the date of first dose of study medication to allow medications to be classified as either Prior, or Concomitant.

Medications that start and stop prior to the date of first dose of study medication will be classified as Prior medication. If a medication stops on or after the date of first dose of study medication up to the last dose of study medication, then the medication will be classified as a Concomitant medication.

If medication start and/or stop dates are missing or partial, the dates will be compared as far as possible with the date of first dose of study medication. Medications will be assumed to be Concomitant, unless there is clear evidence (through comparison of partial dates) to suggest that the medication stopped prior to the first dose of study medication. If there is clear evidence to suggest that the medication stopped prior to the first dose of study medication, the medication will be assumed to be Prior.

Imputation of partial dates of prior and concomitant medications is described in Appendix 4.14 (section 4.14.7).

Prior and concomitant medication will be summarized using the ITT population (Section 4.4.2) separately. Frequency table will be provided by treatment group, anatomical therapeutic chemical (ATC) drug class and preferred term (PT), where ATC and PT will be coded using the World Health Organization-Drug Dictionary Enhanced (WHO-DDE) September 2020 B3.

A by-subject listing of prior and concomitant medications will be provided using the ITT population.

In addition, the following treatments are not permitted from Visit 1 to Visit 4 (end of IMP treatment) or unscheduled Deterioration Visit:

- Expectorants
- Antitussive agents
- Sedatives
- Traditional Chinese Medicine (TCM) treatments.

Prior prohibited medications are defined as those prohibited medications with a stop date on or after the Visit 1 date, and prior to the first dose of study medication date. Prohibited concomitant medications are defined above as for concomitant medications for those treatments not permitted.

Prior prohibited medications and prohibited concomitant medications will be summarized for the ITT population. Frequency tables will be provided following the same structure as for prior and concomitant medications.

A by-subject listing of prohibited medications will be provided using the ITT population.

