4.14.7.2 Algorithm for Adverse Events (include TEAE and pre-treatment AE)

Start/ Increase Severity Date	Stop Date	Action
Known	Known	Considered as a TEAE if start date is on or after the date of the first dose of study drug.
	Partial	Considered as a TEAE if start date on or after the date of the first dose of study drug. The last day of the month and the last month (i.e. December) will be used if the stop day/month is missing.
	Missing	Considered as a TEAE if start date on or after the date of the first dose of study drug.
Partial, but known components show that it cannot be on or after first study drug taken date	Known	Not a TEAE. The first day of the month and January will be used if the start day/month is missing.
	Partial	Not a TEAE. The first day of the month and January will be used if the start day/month is missing. The last day of the month and the last month (i.e. December) will be used if the stop day/month is missing.
	Missing	Not a TEAE. The first day of the month and January will be used if the start day/month is missing.
Partial, could be on or after first study drug taken date	Known	Considered as TEAE, if stop date is after first study drug taken date. The first study drug taken date will be used if start date is in the same month/year with first study drug taken date, or the first day of the month and January will be used if the start day/month is after first of study drug taken date Considered as not TEAE, if stop date is prior to first of study drug

Start/ Increase Severity Date	Stop Date	Action
		taken date. The first day of the month and January will be used if the start day/month is missing.
	Partial	Considered as TEAE. The first of study drug taken date will be used if start date is in the same month/year with first study drug taken date, or the first day of the month and January will be used if the start day/month is after first study drug taken date. The last day of the month and the last month (i.e. December) will be used if the stop day/month is missing.
	Missing	Considered as TEAE. The first study drug taken date will be used if start date is in the same month/year with first study drug taken date, or the first day of the month and January will be used if the start day/month is after first study drug taken date.
<hr/>		
Missing	Known	Considered as TEAE if stop date is on or after the date of the first dose of study drug.

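### SAP 4.14.7.1 can impute a medication start after its stop, so that a drug stopped before first dose meets neither class in its table row, contrary to SAP 4.7

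*SAP*

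**What the plan says.** SAP 4.7 gives the classification rule in the body text. Where dates are missing or partial, a medication counts as Concomitant by default. The exception is evidence of an earlier stop: given "clear evidence to suggest that the medication stopped prior to the first dose of study medication, the medication will be assumed to be Prior". The section then refers to Appendix 4.14.7 for the imputation of partial dates.

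The introduction to 4.14.7 makes its tables binding case by case. In 4.14.7.1, the row for a partial start and a known stop has two branches that impute the first-dose date:

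- Day missing: "the date of first dose of study mediation will be used if only the day of start date is missing", if month and year agree with first dose.
- Day and month missing: "the date of first dose of study mediation will be used if the start day and month is missing", if the year agrees with first dose.

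The same row then assigns the class. For Prior: "If the imputed start date and stop date is prior to the date of first dose of study medication, considered as prior". For Concomitant: "if the stop date is on or after the date of first dose of study medication, considered as concomitant". The row for partial start and partial stop reuses this start rule and the same Prior condition.

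The row for a wholly missing start and a known stop behaves differently: "Start date will not be imputed if stop date is prior to the date of first dose of study medication".

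In the adverse-event table, 4.14.7.2, the cell for a partial start that could fall on or after first dose, with a known stop, reads "Considered as TEAE, if stop date is after first study drug taken date". The cell for a missing start and a known stop reads "Considered as TEAE if stop date is on or after the date of the first dose of study drug".

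**The concern.** The start is imputed without reference to a stop date that is already known. When that stop precedes first dose, the imputed record is impossible (start after stop) and fits neither condition of its row. A record with part of a start date is then handled worse than one with no start date at all.

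At stake is the by-arm frequency table of prior medications in the ITT population (SAP 4.7). Protocol section 12 collects medications used within one month before screening, including antibiotics, and randomisation follows within 7 days of screening. The table therefore covers a period in which a start often shares a calendar month with first dose. A programmer following 4.14.7.1 literally would lose such records; one following 4.7 would keep them. The SAP does not say which governs.

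**Working it through.** The plan states no figure to reproduce, so the check applies the rules literally to an illustrative case: first dose 16 March 2020, last dose 22 March 2020.

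**Inputs.** The imputation and class rules of 4.14.7.1, and the class rule of 4.7, as set out above.

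**One record.** Start March 2020 (day missing), stop 10 March 2020.

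- Imputed start: 16 March, which is after the stop.
- Prior needs imputed start and stop both before 16 March. The start fails.
- Concomitant needs the stop on or after 16 March. The stop fails.
- Result under 4.14.7.1: no class. Result under 4.7: Prior.

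**All stop dates up to 31 March 2020, stop known.**

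| Recorded start | Stops before first dose | Class under 4.14.7.1 | Class under 4.7 |
|---|---|---|---|
| March 2020 | 15 (1 to 15 March) | none for 15 of 15 | Prior |
| 2020 only | 31 + 29 + 15 = 75 | none for 75 of 75 | Prior |
| February 2020 | 29 + 15 = 44 | Prior for 44 of 44 | Prior |
| 2019 only (stops from 1 December 2019) | 31 + 75 = 106 | Prior for 106 of 106 | Prior |

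In every row the 16 stop dates from 16 to 31 March are Concomitant under both rules. The fault is confined to a partial start in the month, or the year, of first dose combined with a stop before first dose.

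**Partial start and partial stop.** Start 2020, stop February 2020: imputed start 16 March, imputed stop 29 February. The record again has no class, while 4.7 makes it Prior.

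**Whether the gap is intended.** The only instruction in 4.14.7.1 to leave the category missing is the note on starts after the last dose, which does not cover this case.

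**After correction.** Imputing 1 March (day missing) or 1 January (year only) puts the start no later than any of the stops above and before 16 March. All 15 and all 75 become Prior, and the 16 later stops stay Concomitant. The partial/partial example becomes 1 January to 29 February, hence Prior.

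**How often a start shares the month of first dose.** The documents give no count of partial dates. Assume that first-dose dates are spread evenly over the calendar and that starts are spread evenly over the days before first dose. For a start d days earlier, the chance of a shared month is about 1 − d/30.4:

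- d = 7: 1 − 7/30.4 = 77%; d = 14: 54%; d = 21: 31%.
- Averaged over the last 30 days (mean d = 15.5): 1 − 15.5/30.4 = 49%.
- Averaged over the last 7 days (mean d = 4): 1 − 4/30.4 = 87%.

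These are chances of a shared month only. Losing the class also needs a missing start day and a stop before first dose.

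**Adverse events.** Take an event with a partial start and a stop on the day of first dose. It is not after first dose, so the TEAE clause of that cell fails. It is not before first dose, so the non-TEAE clause fails too. With the start wholly missing, the same event is a TEAE.

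**The case against.** The strongest reply is that 4.7 already settles the class. It covers missing and partial dates, leaves no such record unclassified, and refers to the appendix for imputing dates, not for replacing its rule. That stands as far as the class goes: the SAP as a whole does not leave these drugs without one. It does not clear the appendix, because the table assigns classes itself, its introduction says its rules apply to each case, and the imputed start still falls after the stop whichever rule governs.

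The effect is also limited. The table is descriptive. The superiority tests stratify on baseline score, and the optional subgroup analyses concern concomitant, not prior, medications. By-subject listings remain and do not show imputed dates. The prior-prohibited table is defined by stop date and is unaffected. All of this stands.

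Three stronger readings are tempting, and the documents do not support them:

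- *The most recent prior treatments drop out of the table.* Recent drugs with a complete start, a wholly missing start, or a partial start in an earlier month (or an earlier year, if only the year is known) are classed correctly.
- *The same-month percentages are the chance of losing the class.* A drug that continues through first dose, such as an ongoing antibiotic, shares the month and is correctly Concomitant.
- *Reactions to the first infusion could be lost from the TEAE tables.* Protocol 20.4.8 presumes an event treatment-emergent when incomplete dates leave this unclear, and SAP 4.12 does not list that default among its changes. The adverse-event cell is a wording mismatch to align.

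**Conclusion.** The point holds as an internal contradiction in the SAP. Read literally, two rows of 4.14.7.1 (partial start with known stop, and partial start with partial stop when the imputed stop precedes first dose) produce a start after the stop and no class. They disagree with 4.7 and with the missing-start row of the same table.

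Within its scope the fault is complete: 15 of 15 and 75 of 75 stop dates in the example. Its effect on the trial is minor. Records leave the by-arm prior-medication table only if the appendix is programmed without regard to 4.7, and the number of records with such dates is unknown. Listings, the prior-prohibited table, efficacy results, type I error and power do not change. The conclusion rests on the wording of the rules; only the same-month percentages rest on an assumption from outside the documents.

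**What to change.** 1. In the partial-start rows of 4.14.7.1, classify on the known or imputed stop date as 4.7 does: a stop before first dose means Prior.
2. Never impute a start later than the stop. When the stop precedes first dose, use the first day of the known month, or 1 January if only the year is known. The adverse-event table already does this for events that stopped before first dose. Impute the first-dose date only when the stop is on or after it.
3. State in 4.7 or 4.14.7 that 4.7 governs the class.
4. In 4.14.7.2, in the cell for a partial start and known stop, change after to on or after the first study drug date, to match the missing-start row and the protocol 20.4.8 default.

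The cost is three table cells, one sentence and the matching derivation code. No data collection or efficacy analysis is affected.
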